5.0 Study Procedures

This is a blinded study. Our research coordinator will present to the OR prior to the surgeon to meet with OR staff. At this time, the coordinator will inform the OR staff which group the patient has been randomly assigned. OR staff will be educated to set the laser as instructed by the surgeon but not share whether the MOSES laser lithotripsy is being used. Surgeons will not be aware of the group assignment. The surgeons are only able to adjust the laser energy settings between 0.4-1.0 joules and 4-15 hertz. To control for stone fragment size, surgeons will have to use an 13 french ureteral access sheath independent of ureteral diameter. The MOSES setting is turned on with a touch pad attached to the laser unit. Once the surgeon is ready to laser fragment the stone, they will request that the laser be activated and provide the laser energy settings. The laser technician/nurse will follow randomization and add or remove the MOSES option. The surgeons will not be informed if they are using standard laser or MOSES augmented laser technology. At the conclusion of laser fragmentation, stone basket extraction will occur and once all fragments are removed, the patient will have a ureteral stent placed, awoken, extubated and transferred to the post anesthesia recovery unit. Objective data about laser settings, utilization time and total energy will be obtained at the conclusion of the case. Additionally, the circulating team will record the total OR time. Other variables of interest include blood loss, blood transfusion requirements and complications (utilizing Clavien-Dindo classification) with an expected rate of approximately 1-2%. Subjective grading of stone movement during laser fragmentation as well as stone migration will be recorded.

In addition to the intraoperative variables mentioned above, we will obtain clinical information including stone size, location, and stone analysis will be recorded.

6.0 Reporting of Adverse Events or Unanticipated Problems involving Risk to Participants or Others

All adverse events or unanticipated problems related to study participation will be reported in keeping with the IRB's guidelines regarding such events.

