8.1 Endpoint Considerations

The primary endpoint of interest will reduction in total laser time and total OR time. Secondary endpoints will evaluate complication rates using the Clavien-Dindo score.

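### Total OR time, a primary endpoint and the basis of the sample size, is recorded by staff who are told the assigned arm before the case

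*Protocol*

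**What the plan says.** Protocol Section 8.1 names two time outcomes as primary: "The primary endpoint of interest will reduction in total laser time and total OR time". Section 8.0 sizes the trial on the second of them, using a difference of up to 10 min in overall OR duration against an average of about 1 hour.

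Section 5.0 opens with "This is a blinded study" and then sets out who knows what:

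- **Surgeons:** "Surgeons will not be aware of the group assignment".
- **OR staff:** the coordinator meets them before the surgeon arrives, and "At this time, the coordinator will inform the OR staff which group the patient has been randomly assigned". Their one restriction is this: "OR staff will be educated to set the laser as instructed by the surgeon but not share whether the MOSES laser lithotripsy is being used".
- **Laser technician or nurse:** this role follows the randomization and switches the MOSES option on or off.

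The same section covers data capture. For the laser it says: "Objective data about laser settings, utilization time and total energy will be obtained at the conclusion of the case". For the other primary outcome it says: "Additionally, the circulating team will record the total OR time".

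**The concern.** The blind described in Section 5.0 is a blind of the surgeon. The instruction to staff not to share the MOSES status protects that blind. It does nothing to keep the person who records the outcome unaware of the arm. A circulating team is ordinarily part of the OR staff, so the people briefed on the arm at the start of the case also write down one of the two primary outcomes at its end.

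A difference between arms could then arise in two ways that have nothing to do with the laser. Staff who expect MOSES to be quicker might note times slightly differently by arm. They might also work slightly faster or slower in those non-laser parts of the case that they influence. Either would add minute for minute to the estimated treatment difference. No analysis can take it out afterwards, so this cannot be left to a statistical analysis plan: who is told and who records are trial procedures, and the protocol fixes them.

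**Working it through.** **Step 1: the text, link by link.**

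| Question | Protocol | Answer |
|---|---|---|
| Is total OR time primary? | 8.1 | Yes, with total laser time |
| Is it the basis of the sample size? | 8.0 | Yes, 10 min on about 1 hour |
| Who is told the arm? | 5.0 | OR staff, before the surgeon arrives |
| Who records total OR time? | 5.0 | The circulating team |
| Who is stated to be unaware? | 5.0 | Surgeons only |
| Is the circulating team exempted, or a blinded recorder named? | nowhere | No |

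One link is an inference: that the circulating team belongs to the OR staff. It is the ordinary reading, and nothing in the protocol separates the two.

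**Step 2: the plan's own figure.** Section 8.0 gives 53 per arm, 80% power, alpha 0.05 and a 10 min difference. It gives no SD and does not say whether the test is one- or two-sided, so 53 cannot be reproduced from stated inputs. It can be solved backwards:

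SD = 10 × √(53/2) / (z for alpha + z for power)

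- Two-sided, normal approximation: 10 × 5.148 / (1.960 + 0.842) = 18.4 min.
- Two-sided, t-test: standardized difference 0.549, so SD = 10 / 0.549 = 18.2 min.
- One-sided: 10 × 5.148 / (1.645 + 0.842) = 20.7 min.

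**Step 3: what a systematic difference would do.** Assume two-sided alpha 0.05, 53 per arm, no true effect, and a constant difference of b minutes between arms from recording or pacing.

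SE = SD × √(2/53). This is 3.57 min for SD 18.4 and 3.54 min for SD 18.2.

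False-positive rate = [1 − Φ(1.960 − b/SE)] + Φ(−1.960 − b/SE)

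Worked for b = 2 and SE = 3.57: b/SE = 0.560. The upper tail is 1 − Φ(1.400) = 0.081, the lower tail is Φ(−2.520) = 0.006, and the sum is 0.087.

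| Assumed b | SD 18.2 | SD 18.4 | SD 20.7 (sized one-sided, tested two-sided) |
|---|---|---|---|
| 0 min | 5.0% | 5.0% | 5.0% |
| 1 min | 5.9% | 5.9% | 5.7% |
| 2 min | 8.7% | 8.7% | 7.9% |
| 3 min | 13.6% | 13.4% | 11.6% |

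The values of b are assumptions, equal to 10%, 20% and 30% of the 10 min target. The protocol gives no evidence on their size or direction.

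**The case against.** The strongest case on the other side is that this is a low-risk exposure. OR time is read from a clock and involves no judgement. The surgeon fragments the stone, removes the pieces and places the stent, and so largely determines how long the case takes. The surgeon is explicitly blinded. A logging discrepancy would more plausibly be about 1 min than 2 or 3, and at 1 min the false-positive rate is only about 5.9%. All of this stands, and it limits the weight of the point. It does not change who records the outcome.

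A reader might infer more than the protocol supports:

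- **That OR time is written down by hand while laser time comes off the machine.** Section 5.0 says only that the team will record OR time, so a system time stamp is neither stated nor excluded. It calls the laser data objective but names neither source nor recorder.
- **That the blinded label gives this outcome no protection.** The surgeon's blind does protect it against bias through the surgeon's own conduct of the case.
- **That the informed staff control wake-up and transfer.** Section 5.0 does not say who carries out these steps, or whether the anaesthesia team is among those told. Pacing is a possible route, not a documented one.
- **That the missing start and stop events are a fault in themselves.** An analysis plan that is not shown may define them, so no weight is placed on this.

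One practical objection also stands. The wording allows the laser to be run by a nurse, who may also be circulating. In such a room the two roles cannot be separated by a narrower briefing alone.

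**Conclusion.** The point holds as a gap in procedure. As written, Section 5.0 lets a primary outcome, the one that sets the sample size, be recorded by people who have been told the arm. This rests on the protocol text and on reading the circulating team as part of the OR staff.

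The likely bias is limited, and nothing in the protocol shows that it would occur or in which direction. The false-positive rates of about 5.9%, 8.7% and 13.5% for 1, 2 and 3 min are illustrations. They depend on a back-solved SD of 18.2 to 18.4 min, a two-sided test and assumed shifts. The point concerns total OR time only. It is worth correcting because the outcome is primary and the correction is cheap; it is not grounds for calling the trial unblinded or its result unreliable.

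**What to change.** Change two sentences in Section 5.0.

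1. **Disclosure.** The coordinator tells the arm only to the laser technician or nurse who sets the MOSES option, not to the OR staff as a group.
2. **Recording.** Total OR time is recorded by a team member who has not been told the arm. Where the laser nurse also circulates, it is taken from routine system time stamps or from the anaesthesia record, with the anaesthesia team not told the arm.

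Keep total OR time as the whole OR duration, for example room-in to room-out. A shorter interval, such as scope insertion to stent placement, would depart from the overall OR duration on which Section 8.0 powers the trial and from the OR-utilization aim in Section 2.0. If time stamps are already in use, saying so in Section 5.0 settles the recording question; the narrower briefing is still worth making because it also covers pacing.

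The cost is a slightly narrower briefing and, in some rooms, reliance on a routine time record that the protocol does not mention and that the site would need to confirm is available. No extra staff, visits or patients are needed, and the endpoint is not redefined.

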7.0 Study Withdrawal/Discontinuation

If a subject wishes to withdraw from the study, he may do so by verbal or written request to the research team. A subject may be withdrawn from the study by a physician-investigator if determined to be in the subject's best interest for medical reasons.

8.0 Statistical Considerations

Overall OR duration may differ up to 10 min with an average OR time for URS estimated at approximately 1 hour. A power analysis with 80% power and an alpha of 0.05 requires a total recruitment of 106 patients with 53 patients in each treatment arm. Due to a 10% chance of withdrawal rate, the study will enroll 116 subjects for 106 subjects to complete the study. Statistical analysis of the obtained data will include a student T-test for comparison of two continuous variables and chi-squared for categorical variables. If enough events occur to warrant a multivariate analysis, a Cox regression utilizing forward selection will be performed.

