4.0 Enrollment/Randomization

Potential subjects will be identified during their pre-operative clinic visit. Physician-investigators will review medical chart and relevant pre-operative testing to make this determination. Potential subjects will then meet with a member of the study team to read the consent in detail and discuss the study in full.

After consent has been obtained, the study personnel obtaining consent will then obtain and assign the appropriate randomization for that subject. The patients will be randomized 1:1 to either standard laser lithotripsy or MOSES laser lithotripsy. Randomization will be performed using the redcap randomization application.

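### Enrolling 116 patients with 10% withdrawal leaves about 104 completers (52 per arm), not the stated 106 (53 per arm)

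*Protocol*

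**What the plan says.** Protocol Section 8.0 (Statistical Considerations) sets out the sample size in three steps.

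- The planning difference: "Overall OR duration may differ up to 10 min with an average OR time for URS estimated at approximately 1 hour".
- The number needed: "A power analysis with 80% power and an alpha of 0.05" "requires a total recruitment of 106 patients with 53 patients in each treatment arm".
- The allowance for withdrawal: "Due to a 10% chance of withdrawal rate, the study will enroll 116 subjects for 106 subjects to complete the study".

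Section 4.0 fixes the allocation: "The patients will be randomized 1:1 to either standard laser lithotripsy or MOSES laser lithotripsy". Section 7.0 describes how a subject may withdraw or be withdrawn but gives no rate. No other section gives a different enrolment figure or withdrawal rate, so the sentence in Section 8.0 has to stand on its own.

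**The concern.** The sentence links three numbers: patients enrolled, the proportion expected to withdraw, and patients completing. Any two of them fix the third. Here the third does not follow from the other two, because a 10% loss from 116 takes away more than the 10 patients that separate 116 from 106.

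Section 8.0 presents 106 as the number the power analysis requires. If 116 are enrolled and 10% withdraw as assumed, the trial is expected to finish slightly below its own requirement. What is at stake is the accuracy of the stated plan and a small amount of power. Estimates, tests, endpoints and conduct are not affected.

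**Working it through.** **Inputs, all from the protocol**

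| Input | Value | Place |
|---|---|---|
| Completers required | 106 (53 per arm) | Section 8.0 |
| Withdrawal | 10% | Section 8.0 |
| Enrolled | 116 | Section 8.0 |
| Power, alpha | 80%, 0.05 (sidedness not stated) | Section 8.0 |
| Allocation | 1:1 | Section 4.0 |

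**Step 1: where 116 comes from.** Adding 10% to the required number gives 106 × 1.10 = 116.6. This becomes 116 only when rounded down; rounded up it is 117.

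**Step 2: the usual inflation.** To expect N completers when a proportion w of those enrolled withdraws, enrol N / (1 − w). Here 106 / 0.90 = 117.8, so 118 (59 per arm). The stated 116 is 2 below this (2/118 = 1.7%).

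**Step 3: what 116 delivers.**

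- Expected completers: 116 × 0.90 = 104.4, or 52.2 per arm.
- Shortfall: 106 − 104.4 = 1.6 patients.
- Expected withdrawals: 116 × 0.10 = 11.6, against the 116 − 106 = 10 that the sentence allows.
- Withdrawal rate at which 116 gives 106: 10 / 116 = 8.6%.

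**Step 4: effect on power.** Section 8.0 gives no standard deviation, so the 53 per arm cannot be re-derived and is taken as given. For a two-sample t-test at alpha 0.05, the standardised difference d that 53 per arm implies was back-solved under two assumptions: that 53 gives exactly 80% power, or that the exact answer was just above 52 and was rounded up to 53.

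| Test | Assumption about 53 per arm | d | Power at 53 | Power at 52 |
|---|---|---|---|---|
| Two-sided | Exactly 80% at 53 | 0.549 | 80.0% | 79.2% |
| Two-sided | Rounded up from just above 52 | 0.555 | 80.8% | 80.0% |
| One-sided | Exactly 80% at 53 | 0.486 | 80.0% | 79.3% |
| One-sided | Rounded up from just above 52 | 0.491 | 80.7% | 80.0% |

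In every row, going from 53 to 52 per arm costs less than one percentage point.

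**Step 5: chance of reaching 106.** If each of 116 subjects withdraws independently with probability 10%, the number completing is binomial with mean 104.4 and standard deviation √(116 × 0.10 × 0.90) = 3.2. The chance that at least 106 complete is about 38%. With 118 enrolled it is about 60%.

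**The case against.** The strongest reply is that the gap is too small to matter. The 10% is a round planning guess, adding 10% on top is a common shortcut, and 116 is within 2 patients of the exact answer. The shortfall of 1.6 is half the standard deviation of the number completing (1.6 / 3.2), and even 118 enrolled would miss 106 about 40% of the time. The power figures also rest on a back-solved effect size, since no standard deviation is given, so they describe the cost of losing one patient per arm and not the trial's real power.

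All of that stands, and it is why the point is minor. It does not make the sentence correct. Reading the 10% as a share of the 106 completers does not rescue it either: 10% of 106 is 10.6, still more than the 10 allowed. Nor can the matter be left to a separate analysis plan, because all three figures are stated in the protocol itself.

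A second reply is that the direct repair is to enrol 118, which keeps both the 10% and the 106. That would be consistent too. It means two more patients, however, to remedy a shortfall that costs under one percentage point of power. Restating the figures puts the record right without them.

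**Conclusion.** The point holds as a minor arithmetic error. On the protocol's own withdrawal rate, 116 enrolled gives about 104 expected completers (52 per arm), 1.6 fewer than the 106 stated. The two totals fit together only if withdrawal is at most about 8.6%.

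The completer count follows from the protocol's figures alone. The power range at 52 per arm (79.2% to 80.0% two-sided, 79.3% to 80.0% one-sided) also assumes that 53 per arm is right for 80% power, either exactly or after rounding up. The finding does not show that the trial is underpowered and should not be used to suggest it.

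**What to change.** Amend the withdrawal sentence in Section 8.0 so that its three figures agree, in one of two ways:

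1. Keep 116 enrolled and 10% withdrawal, and state about 104 expected completers (about 52 per arm). Give the matching power, which should be about 79% to 80%, recomputed by the sponsor from its own design inputs.
2. Keep 116 enrolled and 106 completers, and state that this assumes withdrawal of no more than about 8.6%. The sponsor should be content that this rate is realistic, since the protocol now expects 10%.

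The first keeps the withdrawal assumption as it is. Either one changes a single sentence, needs no extra patients and leaves the conduct of the trial untouched. The only cost is that the stated number of completers, or the stated withdrawal allowance, becomes slightly less favourable.

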3.0 Inclusion/Exclusion Criteria

Inclusion criteria:

- >18 years of age
- Kidney or ureteral stone requiring laser lithotripsy fragmentation

Exclusion criteria:

- < 18 years of age

- Infectious, struvite stones.
- Atypical collecting system anatomy that prolongs the case (ureteral stricture, malrotated kidney, infundibular stenosis, ureteral duplication)

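### The only test named for the two continuous primary endpoints is an unadjusted t-test, which leaves recorded stone size in the error term; adjusting for it would cost almost nothing and may add power

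*Protocol*

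**What the plan says.** Section 8.1 makes two continuous times primary: "The primary endpoint of interest will reduction in total laser time and total OR time". Section 8.0 gives the method: "Statistical analysis of the obtained data will include a student T-test for comparison of two continuous variables". The only multivariable model is conditional: "If enough events occur to warrant a multivariate analysis, a Cox regression utilizing forward selection will be performed".

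The sample size rests on OR time alone: "Overall OR duration may differ up to 10 min with an average OR time for URS estimated at approximately 1 hour". With 80% power and alpha 0.05, the plan "requires a total recruitment of 106 patients with 53 patients in each treatment arm". It states no standard deviation, does not say whether alpha is one- or two-sided, and gives no target difference for laser time.

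On stone size, Section 5.0 says "we will obtain clinical information including stone size, location, and stone analysis will be recorded". Section 1.0 notes that larger and harder stones can be slow to break up, and expects more efficient fragmentation to shorten the operation. Eligibility in Section 3.0 ("Kidney or ureteral stone requiring laser lithotripsy fragmentation") sets no size limit. Section 4.0 describes 1:1 randomization and names no stratification by size.

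**The concern.** The protocol itself describes stone size as a driver of fragmentation time, collects it, and lets it vary freely. Size then enters neither the randomization as described nor the named analysis, so whatever variation it causes in the two times stays in the residual and widens the confidence interval for the treatment difference.

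Sections 3.0 and 5.0 do remove some variation between cases: anatomy that lengthens the procedure and struvite stones are excluded, and sheath size and the range of laser settings are fixed. None of this limits size.

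The Cox model does not fill the gap. It depends on a sufficient number of events, chooses its terms by forward selection, and is not an adjusted comparison of mean times.

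Neither bias nor false-positive error is at stake. What is at stake is power for a difference that Section 8.0 describes as at most 10 minutes, so the true difference may well be smaller than the one used for planning.

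**Working it through.** **Inputs from the protocol.** 53 per arm, 80% power, alpha 0.05, difference 10 min in OR time (Section 8.0).

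**Inputs assumed.** The sidedness of alpha (both cases shown), and R², the share of within-arm variance in OR time explained by stone size (0 to 0.5).

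**1. The plan's own figure.** Without a standard deviation, 106 cannot be derived forwards, so the calculation is run backwards with the noncentral t distribution on 2 × 53 − 2 = 104 degrees of freedom. The noncentrality is d × √(53/2), where d is the difference divided by the SD.

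- Two-sided 0.05: 80% power needs d = 0.549, so SD = 10/0.549 = 18.2 min.
- One-sided 0.05: d = 0.486, so SD = 10/0.486 = 20.6 min.

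**2. Adding one covariate.** The residual SD becomes SD × √(1 − R²). One degree of freedom is spent (104 to 103). Chance imbalance in size inflates the variance by 1 + 1/102 on average. The noncentrality is then

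d × √(53/2) / √[(1 − R²)(1 + 1/102)].

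Example, two-sided, R² = 0.2: 0.549 × 5.148 = 2.83; √(0.8 × 1.0098) = 0.899; 2.83/0.899 = 3.15, which gives 87.6% power.

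The width of the confidence interval relative to the t-test is approximately √[(1 − R²)(1 + 1/102)].

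| R² | Power for 10 min, two-sided | Power for 10 min, one-sided | Difference detectable at 80% power (two-sided) | Relative interval width |
|---|---|---|---|---|
| t-test | 80% | 80% | 10 min | 1 |
| 0 | 79.6% | 79.7% | 10.05 min | 1.005 |
| 0.05 | 81.6% | 81.4% | 9.80 min | 0.98 |
| 0.1 | 83.6% | 83.2% | 9.53 min | 0.95 |
| 0.2 | 87.6% | 86.9% | 8.99 min | 0.90 |
| 0.3 | 91.5% | 90.5% | 8.41 min | 0.84 |
| 0.5 | 97.6% | 96.8% | 7.11 min | 0.71 |

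**3. Break-even.** Adjusted power equals 80% at R² of about 0.01, a correlation of about 0.10.

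**4. Check by simulation** (20,000 trials per setting). With normal stone size and normal errors, adjusted power over the same six R² values was 79.6, 81.6, 83.9, 87.6, 91.5 and 97.4%, with type I error 4.6–5.0%. With right-skewed size (lognormal) and right-skewed errors (gamma), analysed in untransformed minutes, it was 79.6, 81.6, 83.4, 87.4, 91.5 and 97.8%, with type I error 4.8–5.1%. In a separate simulation of 5,000 trials at a correlation of 0.5 (R² = 0.25), type I error was 4.9% for both methods and power was 81% for the t-test against 90% for the adjusted model.

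**5. Laser time.** No power figure is possible, because the protocol gives neither a difference nor an SD for it.

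**The case against.** The strongest case against is that nothing here is wrong. A t-test under 1:1 randomization is unbiased and fits a sample size apparently built on two means. The wording of Section 8.0 is not exclusive, and covariates are usually settled in an analysis plan, which may exist. The benefit rests on an SD and an R² that the protocol does not give. The evidence and the arithmetic also concern different endpoints: the remark in Section 1.0 is about fragmentation, hence mainly laser time, while every power figure is for OR time, which also includes basket extraction and stent placement. Finally, Section 5.0 does not say when or how size is measured, and missing or inconsistent sizes could cost more than one degree of freedom.

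Much of this stands. The test is valid, the gain is unknown, the link to OR time is less direct than the link to laser time, and the upper rows of the table are not forecasts. The measurement point is fair and has to be part of the fix.

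It does not remove the point. Section 8.0 names a method rather than staying silent, and that method makes no use of a variable which the protocol both collects and describes as affecting fragmentation time. The balance is lopsided: adjustment loses about 0.4 percentage point of power if size is uninformative and gains once size explains more than about 1% of the variance. Naming the covariate in advance also prevents its being chosen after the data are seen.

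**Conclusion.** The concern holds as a matter of efficiency, not validity, and the change should be made. The possible gain in power for OR time runs from under 2 percentage points at R² = 0.05 to about 11 or 12 at R² = 0.3, depending on sidedness. These figures assume the back-solved SD, a roughly linear relation with size, and complete size data. Confidence is medium, because nothing in the protocol fixes R². For laser time the protocol's reasoning supports adjustment most directly, but the size of the gain cannot be stated.

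**What to change.** In Section 8.0, state that the primary comparison of total OR time and of total laser time, each in minutes, is a linear model with treatment and pre-operative stone size, and that the unadjusted t-test is a sensitivity analysis.

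Say that stone size is the measurement taken before surgery, and define how it is taken, including when there is more than one stone. This is practical, since Section 4.0 already has test results reviewed before consent and randomization: "Physician-investigators will review medical chart and relevant pre-operative testing to make this determination".

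Do not adjust for stone analysis unless it is known before randomization. Add location only if a few categories are fixed in advance, since the protocol does not say that it predicts either time.

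The cost is one or two sentences in Section 8.0 plus the measurement rule, with no extra patients, visits or variables. The statistical cost is about 0.4 percentage point of power if stone size proves uninformative. Size must be complete for all randomized patients if none are to drop out of the model.

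### The unadjusted t-test fixed for laser time and OR time is valid, but it gives up precision that surgeon, stone size and stone location could supply

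*Protocol*

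**What the plan says.** - **Analysis (Section 8.0).** The analysis "will include a student T-test for comparison of two continuous variables". The only multivariable model is a Cox regression with forward selection. It depends on enough events occurring, and its covariates are not named.
- **Endpoints (Section 8.1).** Total laser time and total OR time are primary. Both are continuous, so the t-test applies to both.
- **Operators (Section 5.0).** Surgeons appear in the plural, without a number. The operating surgeon gives the settings within limits: "The surgeons are only able to adjust the laser energy settings between 0.4-1.0 joules and 4-15 hertz". Stone size, location and stone analysis are to be recorded. The surgeon's identity is not on the list.
- **Allocation (Section 4.0).** The ratio is 1:1, assigned after consent. "Randomization will be performed using the redcap randomization application". No stratification factor is named.
- **Sample size (Section 8.0).** "A power analysis with 80% power and an alpha of 0.05 requires a total recruitment of 106 patients", split equally at 53 per arm. The planning difference in OR time is at most 10 min, against a mean of roughly 60 min. No SD, sidedness or between-surgeon variance is given.

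**The concern.** Operating time and laser time plausibly depend on who operates, how large the stone is and where it lies. The permitted settings run from 0.4 J × 4 Hz = 1.6 W to 1.0 J × 15 Hz = 15 W, so operators have room to differ. The protocol already tries to limit such variation: it caps the settings, requires one access-sheath size and excludes anatomy that lengthens the case. Whatever variation remains goes into the error term of a plain t-test.

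The stake is the width of the confidence interval for both primary endpoints. In a trial of 106 completers, a modest gain in precision is worth having when it needs no extra patients and almost no extra data.

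**Working it through.** **Inputs.** From Section 8.0: difference 10 min, 53 per arm, power 80%, alpha 0.05. Assumed, because the protocol does not say: a two-sided test, the share of OR-time variance that the covariates explain (R², 0 to 30%), and 2 to 6 surgeons.

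**Step 1: the plan's own figure.** Without an SD, 53 per arm cannot be reproduced directly. Solving the two-sided t-test power equation for the SD gives 10/0.5493 = 18.2 min (18.4 min by the normal approximation; 20.7 min by that approximation if one-sided). The standard error of the difference is then 18.2 × √(2/53) = 3.54 min.

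**Step 2: adjustment with arms balanced on the covariates.** Residual SD = 18.2 × √(1 − R²), and SE = residual SD × √(2/53). Power comes from the noncentral t.

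| R² | residual SD (min) | SE (min) | power | n per arm for 80% |
|---|---|---|---|---|
| 0 | 18.20 | 3.54 | 80% | 53 |
| 5% | 17.74 | 3.45 | 82% | 51 |
| 10% | 17.27 | 3.35 | 84% | 48 |
| 20% | 16.28 | 3.16 | 88% | 43 |
| 30% | 15.23 | 2.96 | 92% | 38 |

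The lost degrees of freedom (104 − q for q added coefficients) change power by less than 0.1 point.

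**Step 3: allowance for chance imbalance.** If allocation ignores the covariates, q added coefficients inflate the SE by about √(105/(105 − q)). With four surgeons (3 coefficients), stone size (1) and a two-level location (1), q = 5. The factor is √(105/100) = 1.025, and the SE at R² = 0 becomes 3.54 × 1.025 = 3.62 min. Averaged over random allocations, power is:

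| R² | 0 | 5% | 10% | 20% | 30% |
|---|---|---|---|---|---|
| full model, four surgeons | 78% | 80% | 82% | 86% | 90% |

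The cost when the covariates explain nothing is about 0.4 point per coefficient. Surgeon alone costs 0.4 to 1.2 points with two to four surgeons and 2.0 with six. The full model costs 1.2 points with two surgeons, 2.0 with four and 2.9 with six. Adjustment breaks even at R² of about q/105, which is 5/105 = 4.8% for q = 5.

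**Step 4: validity.** Simulations of 106 patients with 3 or 5 surgeons and surgeon shares of 0 to 30% gave the following.
- *Allocation ignoring surgeon:* type I error of the plain t-test was 4.4% to 5.4%, and power stayed near 80%. The surgeon-adjusted model reached 82–83%, 86–87% and 91% at shares of 10%, 20% and 30%.
- *Allocation stratified by surgeon, plain t-test kept:* type I error fell to 2.4–3.0% at a share of 20% and 1.6–2.0% at 30%. With surgeon in the model it was 4.4–4.7%.

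No figure can be given for laser time, because the protocol states no planning values for it.

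**The case against.** The strongest reply is that nothing here is an error. A t-test after 1:1 randomization is valid. The wording on the test is not exclusive, and a separate analysis plan might add covariates. If the planning SD was a total SD, variation between surgeons is already inside the stated 80%. The size of the gain rests wholly on assumed shares, and a wide permitted range of settings does not show that surgeons differ, since settings may follow the stone.

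Most of this stands, and it rules out several stronger readings that a reader might infer:

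- **That the standard errors are wrong or the result biased.** Under allocation that ignores surgeon, 3.54 min is the true sampling error of the unadjusted estimate.
- **That power is below 80%.** The figures show a possible gain over the plan, not a shortfall.
- **That allocation is known to be unstratified.** The protocol is silent on strata and blocks.
- **That chance imbalance invalidates the comparison.** The t-test's error rate already covers it. A half-and-half factor explaining 10% of variance differs by 2 × 18.2 × √0.10 = 11.5 min between levels. A 10-point imbalance therefore moves the estimate by about 1.2 min, a third of one SE.
- **That surgeon-stratified blocks are needed.** Nothing says the surgeon is fixed when allocation follows consent, small blocks within surgeon may be easier to predict, and the model gives most of the gain without them.

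What does not stand is that this is only silence left to a later document. Section 8.0 names the test for continuous variables, and it is unadjusted. The conditional Cox model does not replace it.

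**Conclusion.** The point holds as a loss of efficiency, not of validity. If surgeon, stone size and location together explain 10% to 30% of OR-time variance, adjustment would give about 84% to 92% power with balanced arms, or about 82% to 90% with four surgeons and chance imbalance, against 80% for the t-test. At 5% the gain lies between nothing and two points; at zero there is a loss of about one to three points for the full model, depending on the number of surgeons. These figures assume an SD of 18.2 min and a two-sided test. The variance shares and the number of surgeons are assumptions that the sponsor can check against its own case records. A change is worth making, but the trial can be interpreted without it.

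**What to change.** 1. In Section 8.0, replace the t-test for total laser time and total OR time with a prespecified linear model: treatment, pre-operative stone size, stone location, and operating surgeon as a fixed effect with low-volume surgeons grouped. Report the adjusted difference with its confidence interval.
2. Add the operating surgeon to the variables recorded under Section 5.0.
3. Do not adjust for the laser settings used: they are chosen after randomization.
4. Stratifying the REDCap list by surgeon is optional, and only possible if the surgeon is known at allocation. If it is done, keep surgeon in the model, because a plain t-test would then be conservative.

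The cost is a sentence or two in Section 8.0, one field on the case form and a few degrees of freedom. About 0.4 point of power is lost for each coefficient that turns out uninformative, which is the reason to group surgeons and keep the model short. No patients are added.
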